**FOOTNOTES FOR TABLE 2-1 (See Sections 9 and 10 for additional information)**

 Cycle length is 21 days. If a dose of either study drug is delayed, shift scheduled assessments accordingly.

 EOT Visit occurs 30 days (+7 days) after the last dose of study drug (ADU-S100 or standard of care [pembrolizumab]) or prior to commencing new anti-cancer therapy.

 Safety Follow-up to complete required Safety Reporting Periods (Table 10-1), as indicated. Concomitant medications will only be collected if associated with the management of an ongoing AE or SAE, or if a new anti-cancer treatment. Following EOT, subject may be contacted by phone to complete SAE reporting period as applicable.

-  **Demographics, Medical History, Height:** includes date of birth, age, gender, ethnicity, and race. Medical history includes all active conditions and any condition considered to be clinically significant by the Investigator. Disease-specific details include date of diagnosis, primary tumor histology, prior surgery(ies), radiation therapy, chemo- and biological therapies, and stage of cancer. Obtain standing height.
-  **Tumor imaging:** See [Section 10.2.1](#). Collect scans electronically; perform response assessments per RECIST 1.1 and iRECIST. Tumor assessments should be fixed according to calendar, regardless of treatment delays. After 27 weeks, the imaging frequency for all subjects will be performed at a Q12W (-14 days) frequency until confirmed disease progression, withdrawal, or study end. Perform at EOT if more than 6 weeks have passed since last evaluation.
-  **Vital Signs:** Blood pressure, pulse, respiratory rate, and temperature. Cycles 1 and 2: scheduled time points relative to the start of the pembrolizumab infusion (Day 1) = pre-dose, end of infusion (+30 minutes); scheduled time points relative to the start of the ADU-S100 injection (Days 1, 8) = pre-dose, 3 hour ( $\pm 30$  minutes) and 6 hours ( $\pm 30$  minutes) post-dose. On all other dosing days, perform vital sign assessment prior to the start of each study drug or more frequently as clinically indicated.
-  **Physical Examination:** Complete physical examinations at Screening and EOT; all other indicated visits are symptom-directed physical examinations. Weight at each indicated visit. Assessment may be done up to 3 days prior to visit.

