### 12.5.2 Secondary Efficacy Endpoints

Secondary efficacy endpoints are defined as:

**Overall Survival (OS)** is defined as the time from first dose of study drug until date of death due to any cause. Subjects without documentation of death at the time of analysis will be censored as of the date the subject was last known to be alive.

**Progression-free survival (PFS)** is defined as the time from first dose of study drug to first documentation of disease progression or death due to any cause. Subjects who do not experience progressive disease and are alive will be censored at the time of last evaluable tumor assessment.

**Duration of response (DOR)** is defined as the time from the first tumor assessment that supports the subject's objective disease response to the time of disease progression or death due to any cause.

**Disease control rate (DCR)** is defined as subjects with CR, PR, or stable disease (SD).

**Duration of disease control (DODC)** is defined as the time from the first tumor assessment that supports the subject's disease control (CR, PR, SD) to the time of disease progression or death due to any cause.

**ORR** per iRECIST

RECIST v1.1 and iRECIST will be used for all secondary efficacy endpoints, as applicable. Estimates of PFS and OS will be assessed using Kaplan-Meier methodology.

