**Figure 1 ADU-CL-20 Study Design**

Subjects will be requested to complete multiple clinic visits during all dosing cycles. An end of treatment (EOT) visit will occur 30 (+7) days after the last dose of study drug. All EOT visit assessments will be completed prior to commencing any new anti-cancer therapy.

After completion of the EOT visit, follow-up visits will be conducted at 8-week intervals to satisfy protocol-specified safety reporting periods, and collect data on any subsequent cancer-related therapies as well as vital status. Follow-up visits may be conducted at the site or via telephone call, as appropriate.

Subjects who discontinue study drug early for reasons other than progressive disease will complete the EOT visit and will be asked to continue tumor response assessments. Follow-up visits will also be conducted at 8-week intervals for these subjects.

All study visits (and visit windows), assessments, and procedures will be performed as indicated in [Appendix A: Schedule of Events](#). On days when the study drug is administered, assessments will be performed prior to dosing unless otherwise specified.

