#### 6.5.1.2 *Secondary Efficacy Variables*

Secondary efficacy endpoints include the following:

- Overall Survival (OS): defined as the time from first dose of either study drug until date of death due to any cause. Subjects without documentation of death at the time of analysis will be censored as of the date the subject was last known to be alive.
- Progression-Free Survival (PFS): defined as the time from first dose of either study drug to first documentation of disease progression or death due to any cause. Subjects who do not experience progressive disease and are alive at the time of analysis will be censored at the time of last evaluable tumor assessment. Subjects who receive anti-cancer therapy prior to documented disease progression will be censored on the date of last evaluable tumor assessment on or prior to the start date of the anti-cancer therapy. Subjects with no on-treatment tumor assessments will be censored on the date of treatment start.
- Duration of Response (DOR): defined as the time from the first tumor assessment that supports the subject's objective disease response to the time of disease progression or death due to any cause. Subjects who have ongoing response at the time of analysis will be censored at the time of last evaluable tumor assessment. Subjects who receive anti-cancer therapy prior to documented disease progression will be censored on the date of last evaluable tumor assessment on or prior to the start date of the anti-cancer therapy. Subjects with no on-treatment tumor assessments will be censored on the date of treatment start.
- Disease Control Rate (DCR): defined as the proportion of subjects with CR, PR, or stable disease (SD).

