**Table 3 Censoring Rules for OS, PFS, DOR, and DODC**

Endpoint	Situation	Date of Censoring
OS	No documentation of death	Date that the subject was last known to be alive
PFS, DODC	No progression and no death	Date of last evaluable tumor assessment
PFS, DODC	Anti-cancer therapy prior to documented disease progression	Date of last evaluable tumor assessment on or prior to the start date of the anti-cancer therapy
PFS, DODC, DOR	No on-treatment tumor assessment	Date of treatment start
DODC	Ongoing disease control at time of analysis	Date of last evaluable tumor assessment
DOR	Ongoing response	Date of last evaluable tumor assessment

No other missing data will be imputed.

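### The SAP's Day-1 censoring rule for PFS rests on an undefined term and makes no exception for documented progression or death

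*SAP*

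**What the plan says.** SAP 6.5.1.2 defines PFS as "defined as the time from first dose of either study drug to first documentation of disease progression or death due to any cause". Protocol 12.5.2 has the same event: "time from first dose of study drug to first documentation of disease progression or death due to any cause". On censoring, the protocol has one rule: "Subjects who do not experience progressive disease and are alive will be censored at the time of last evaluable tumor assessment".

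The SAP adds two further PFS censoring rules. One concerns new anti-cancer therapy before progression. The other is the rule at issue: "Subjects with no on-treatment tumor assessments will be censored on the date of treatment start". The same sentence appears in the DOR and DODC bullets. Table 3 carries it as the row "No on-treatment tumor assessment" for PFS, DODC and DOR. The first PFS/DODC row of that table is expressly limited to "No progression and no death"; the on-treatment row has no such limit.

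On scans after the last dose, Protocol Table 2-1, footnote 5, says: "Perform at EOT if more than 6 weeks have passed since last evaluation". The schedule in SAP Appendix A repeats this. SAP 6.1 adds that subjects who stop early for reasons other than progression "will complete the EOT visit and will be asked to continue tumor response assessments".

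**The concern.** The rule turns on whether a scan was on-treatment, not on whether a post-baseline scan exists or an event has been observed. The plan itself schedules scans after the last dose, so the two can differ. The subjects caught would be early failures: those who stop before the first scheduled scan and are then shown to have progressed, or who die first. They stay in the analysis because SAP 7.4.1 bases efficacy on the All Treated Population. Censoring them on Day 1 removes them from the risk set before any event can count, which can only push the Kaplan-Meier PFS curve up.

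The rule also departs from the protocol. SAP section 4 undertakes to explain such differences, but SAP 7.6 does not mention this one.

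**Working it through.** The documents give no PFS figure and no count of early stoppers, so there is no stated number to reproduce. The check has four steps.

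**1. Can the case arise?** Nominal dosing days follow from 21-day cycles with injections on Days 1 and 8. EOT is last dose + 30 to + 37 days. The first scheduled scan is Cycle 4 Day 1 = Day 64, window −7, so Day 57 to 64. The baseline scan may fall anywhere from Day −28 to Day −1. An EOT scan is required if more than 42 days have passed since the last evaluation.

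| Last dose | Day | EOT day | Days since baseline scan, if on Day −1 | If on Day −28 |
|---|---|---|---|---|
| C1D1 | 1 | 31–38 | 31–38 | 58–65 |
| C1D8 | 8 | 38–45 | 38–45 | 65–72 |
| C2D1 | 22 | 52–59 | 52–59 | 79–86 |
| C2D8 | 29 | 59–66 | 59–66 | 86–93 |
| C3D1 | 43 | 73–80 | 73–80 | 100–107 |
| C3D8 | 50 | 80–87 | 80–87 | 107–114 |

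With EOT at its nominal time and no earlier post-baseline scan, the EOT scan is always required after a stop at C2D1 or later. After a Cycle 1 stop it depends on the baseline date. EOT may be brought forward if new therapy is about to start, and the scan might then not be due. Protocol section 10 places EOT assessments before new therapy, so the new-therapy rule does not already remove a progression seen there.

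**2. What do the rules give?**

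- Last dose Day 29, progression first seen at the EOT scan on Day 59 to 66. Under both PFS definitions this is an event on the scan date. Under the literal Table 3 row it is censored on Day 1.
- Death before any scan. Under both definitions this is an event on the date of death. Under the row it is censored on Day 1. This holds even if on-treatment is read as post-baseline.
- DODC: last dose Day 29, stable disease first seen at EOT. The SAP counts DODC from the baseline scan, but the row censors at treatment start, 1 to 28 days later, although control was observed to about Day 60. This is lost follow-up.
- DOR: a subject with no scan cannot be a responder. A responder first seen after the last dose would, on the literal reading, be censored before the response began. The row serves no purpose for DOR on either reading.

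**3. Effect on Kaplan-Meier PFS.** Let k of N subjects have such early events, with no other subject censored before the last of them. After that time:

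- counted as events: S(t) = ((N − k)/N) × S_rest(t)
- censored on Day 1: S(t) = S_rest(t)
- ratio: N/(N − k)

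N = 20 comes from Protocol 12.1. That figure counts evaluable subjects, so the All Treated number may differ. The value of k is assumed.

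**4. Illustration.** Assumptions: k events at 1.6 months; the other event times at evenly spaced exponential quantiles starting at 2.1 months with a median of 6 months; no other censoring.

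| k | Factor | 6-month PFS, events | 6-month PFS, Day-1 censored | Median (months), events | Median (months), Day-1 censored |
|---|---|---|---|---|---|
| 1 | 20/19 = 1.053 | 0.45 | 0.47 | 5.4 | 6.0 |
| 2 | 20/18 = 1.111 | 0.45 | 0.50 | 5.1 | 5.7 |
| 3 | 20/17 = 1.176 | 0.40 | 0.47 | 4.8 | 6.0 |
| 4 | 20/16 = 1.250 | 0.40 | 0.50 | 4.5 | 5.7 |

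If the assumed median in the others is 3 months, 6-month PFS moves only from 0.05 to between 0.05 and 0.06. The relative factor is the same; the absolute shift depends on the level of the curve. At k = 0 there is no effect.

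**The case against.** The best defence is that on-treatment was meant as post-baseline. The same SAP bullet defines the event as first progression or death, and first censors only subjects who have not progressed and are alive. Table 3 sits under the heading on dropouts and missing data, which suits a row for subjects never scanned after baseline. On that reading a progression at EOT counts as an event.

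This stands in part: the documents do not show that observed progressions will be discarded. But elsewhere (SAP 7.1.2 and 7.5.4, for example) the SAP writes post-baseline when it means that, and SAP 7.5.3 names a post-treatment period separately, so a programmer could fairly take on-treatment as narrower. The benign reading also leaves the death case unresolved.

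Reach is limited too. Protocol 10.2.1.1 asks for prompt imaging on deterioration and allows dosing while progression is confirmed, so many early progressors would be scanned on treatment. Only the narrowest meaning, first to last dose, would also catch a subject last dosed at C3D8 whose Day 57 to 64 scan shows progression; the schedule places that scan in the Treatment Period. The continued scanning described in SAP 6.1 is not in the current protocol's footnote 5, although the EOT scan is in both documents.

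Finally, PFS is secondary and SAP 7.4.6.6 calls the results descriptive with no formal comparisons. That bears on importance, not on whether the rule is sound.

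**Conclusion.** The concern holds as a defect of drafting that can change a reported result. An undefined term, a row with no exception for progression or death, and no precedence between rows together allow two defensible programs to give different PFS estimates. The literal one contradicts the endpoint definition in both documents. Any bias is upward, by N/(N − k): 5% to 25% in relative terms for an assumed k of 1 to 4 of 20, and none at k = 0.

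A reader might infer three stronger things that the documents do not support:

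- That PFS will be overstated by a particular number of points. This needs k and the shape of the curve, and neither is given.
- That DODC is overstated in the same way. A subject whose only post-baseline scan shows progression never had disease control and so has no DODC. The DODC effect is confined to lost follow-up when stable disease is first seen at a post-treatment scan.
- That the DOR entry adds non-responders as censored records. DOR starts at the scan supporting response, so a non-responder has no start date.

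The point should be corrected, but it does not touch the primary endpoint.

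**What to change.** - In the PFS and DODC bullets of SAP 6.5.1.2 and in Table 3, replace the condition with: no evaluable post-baseline tumor assessment (including EOT, unscheduled and post-treatment scans) and no documented progression or death. Changing on-treatment to post-baseline alone is not enough, because a subject who dies before any scan would still be censored on Day 1.
- State the precedence: documented progression at any such scan, or death, is an event on its date unless the new anti-cancer therapy rule applies first.
- Remove DOR from the Table 3 row and delete the sentence from the DOR bullet.
- Record the Day-1 rule in SAP 7.6 as an addition to Protocol 12.5.2.

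The cost is a few lines of SAP text and the matching program specification. The plan already schedules the EOT scans and requires deaths to be reported, so no new data are needed. The one downside for the sponsor is that reported PFS may be slightly less favourable.

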KEYNOTE-048 was a randomized, active-controlled, open-label study in adults with metastatic or recurrent HNSCC in the first-line setting. Interim analyses demonstrated pembrolizumab (administered as monotherapy or with platinum/5-fluorouracil) significantly improved OS relative to cetuximab/platinum/5-fluorouracil in populations with tumor and/or surrounding cells with high levels of PD-L1 expression (combined positive score [CPS]  $\geq 20$ ; median 14.9 vs 10.7 months;  $p = 0.0007$ ) and in populations with lower degrees of PD-L1 expression (CPS  $\geq 1$ ; median 12.3 vs 10.3 months;  $p = 0.0086$ ) ([Burtness et al. 2018](#); [Rischin et al. 2019](#)). There were no statistically significant differences in progression-free survival (PFS). In this trial, pembrolizumab showed a lower objective response rate (ORR) than cetuximab/platinum/5-fluorouracil although responses were more durable (CPS  $\geq 1$ , patients treated with pembrolizumab had an ORR of 19.1% and median duration of response 20.9 months; patients treated with cetuximab/platinum/5-fluorouracil had an ORR of 34.9% and median duration of response 4.5 months). The data support pembrolizumab monotherapy as a new first-line standard of care for patients with recurrent or metastatic HNSCC ([Burtness et al. 2018](#); [Rischin et al. 2019](#)).

Immune checkpoint inhibitors such as pembrolizumab have demonstrated significant improvements in duration of response and long-term survival compared to traditional chemotherapy or other standards of care. However, a significant percentage of patients are either nonresponsive to these immunotherapies, most likely due to innate immunosuppressive mechanisms within the TME, or experience disease relapse following an acquired means of immune escape ([Chen et al. 2016](#)). This highlights the need for new, additional therapies with novel mechanisms to fill these treatment gaps.

This clinical trial is designed to evaluate the efficacy and safety of ADU-S100 administered with the checkpoint inhibitor, pembrolizumab, in HNSCC with lesions amenable to intratumoral injection, and for which PD-1/L1 inhibitor therapy is standard of care.

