## 6.5 **Efficacy and Safety Variables**

### 6.5.1 *Efficacy Variables*

#### 6.5.1.1 *Primary Efficacy Variable*

The primary efficacy endpoint is the objective response rate (ORR) defined as the proportion of subjects in whom a complete response (CR) or a partial response (PR) is observed. The Response Evaluation Criteria in Solid Tumors (RECIST) v1.1 will be used to evaluate the primary efficacy endpoint. All responses will be confirmed at the subsequent tumor assessment.

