- Duration of Disease Control (DODC): defined as the time from the first tumor assessment that supports the subject's disease control (CR, PR, SD) to the time of disease progression or death due to any cause; if the subject has a best response of SD, then DODC is calculated from date of baseline tumor assessment to the time of disease progression or death due to any cause. For subjects who have ongoing disease control at the time of analysis, their DODC will be censored at the time of last evaluable tumor assessment. Subjects who receive anti-cancer therapy prior to documented disease progression will be censored on the date of last evaluable tumor assessment on or prior to the start date of the anti-cancer therapy. Subjects with no on-treatment tumor assessments will be censored on the date of treatment start.
- ORR per modified RECIST v1.1 for immune-based therapeutics (iRECIST), where all noted disease progression will be confirmed at the subsequent tumor assessment
- Occurrence and severity of treatment-emergent adverse events
- Changes from baseline in safety assessments
- Plasma concentration-time profiles and derived noncompartmental PK parameters (including  $C_{max}$ , area under curve [AUC])

Progression-free survival, DOR, DCR, and DODC will be determined per RECIST v1.1 and iRECIST. [Section 7.4.6.2](#) contains a full table of the censoring rules that will be used in these analyses. [Section 7.4.6.3](#) contains additional information regarding response assessment per iRECIST. [Section 7.4.6.8](#) contains additional information regarding subgroup analysis.

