#### 7.4.5 *Secondary Endpoint Analysis Methods*

The calculation of ORR and accompanying CI will be repeated for the EAS. The secondary efficacy endpoints described in [Section 6.4.1.2](#) will be summarized for the All Treated Population.

Overall survival and PFS will be analyzed with standard survival methods (Kaplan-Meier estimates) to include the number of subjects who are alive at data cut-off, number of subjects censored, percentiles (including 95% CIs determined by the Brookmeyer and Crowley method) and range. Kaplan-Meier summaries, including graphs of survival curves, will be generated for all subjects receiving study drug.

Progression-free survival at 6, 12, and 24 months (including 95% CIs determined by Greenwood’s formula), DOR, and DODC will be analyzed with the same statistical methodologies as applied to OS.

DCR will be calculated along with accompanying CIs, similar to ORR.

Censoring rules for the analysis of each endpoint are described in [Section 7.4.6.2](#). Subgroup analysis is described in [Section 7.4.6.8](#).

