**Table 4 Scenarios of Assignments of Best Overall Response using iRECIST**

	Timepoint Response 1	Timepoint Response 2	Timepoint Response 3	Timepoint Response 4	Timepoint Response 5	iBOR
Ex. 1	iCR	iCR, iUPD, or NE	iCR, iUPD, or NE	iUPD	iCPD	iCR
Ex. 2	iUPD	iPR, iSD, or NE	iCR	iCR, iUPD, or NE	iCR, iPR, iSD, iUPD, iCPD, or NE	iCR
Ex. 3	iUPD	iPR	iPR, iSD, iUPD, or NE	iPR, iSD, iUPD, NE, or iCPD	iPR, iSD, iUPD, NE, or iCPD	iPR
Ex. 4	iUPD	iSD or NE	iPR	iPR, iSD, iUPD, or NE	iPR, iSD, iUPD, iCPD, NE	iPR
Ex. 5	iUPD	iSD	iSD, iUPD, or NE	iSD, iUPD, iCPD, or NE	iSD, iUPD, iCPD, NE	iSD
Ex. 6	iUPD	iCPD	Any	Any	Any	iCPD
Ex. 7	iUPD	iUPD (no iCPD)	iCPD	Any	Any	iCPD
Ex. 8	iUPD	NE	NE	NE	NE	iUPD

Abbreviations for Table 4: iBOR = immune best overall response; iCPD = immune confirmed progressive disease; iCR = immune complete response; iPR = immune partial response; iSD = immune stable disease; iUPD = immune unconfirmed progressive disease; NE = not evaluable

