## **7.6 Changes in the Conduct of the Study or Planned Analyses**

Section 12.3 (“Analysis Sets”) of the protocol states the following:

*Evaluable Analysis Set (EAS): All subjects who received any amount of study drug and have at least one evaluable response assessment or were discontinued due to toxicity. The EAS will be used for analysis of the primary efficacy endpoint and clinical activity.*

- The EAS will also include subjects who died or discontinued due to clinical progression or toxicity.
- The All Treated Population will be used for analysis of the primary efficacy endpoint and clinical activity. The All Treated Population is identical to the Safety Population that is described in the protocol.
- For RECIST response SD in the calculation of DODC, duration of SD is calculated from date of baseline tumor assessment to the time of disease progression or death due to any cause. The protocol specifies to calculate this duration “from the first tumor assessment that supports the subject’s disease control” for all associated RECIST responses. This SAP further clarifies that the baseline tumor assessment can be taken as the date “supporting” the period of stable disease.

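### Duration of disease control starts at the baseline scan for best response SD but at the first supporting on-study scan for CR or PR, so for the same end date SD records 56 to 90 more days

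*SAP*

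**What the plan says.** Protocol 12.5.2 has one rule for all categories. DODC runs from the first assessment that supports "disease control (CR, PR, SD) to the time of disease progression or death due to any cause".

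SAP 6.5.1.2 repeats that rule and then makes an exception: "if the subject has a best response of SD, then DODC is calculated from date of baseline tumor assessment". Subjects whose best response is CR or PR stay on the general rule. A baseline scan cannot show CR or PR, so the natural reading is that their clock starts at an on-study scan.

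SAP 7.6 lists this as a change from the protocol: "For RECIST response SD in the calculation of DODC, duration of SD is calculated from date of baseline tumor assessment". Its reason is that the baseline scan may count as supporting the period of stable disease: "This SAP further clarifies that the baseline tumor assessment can be taken as the date". It does not extend the baseline origin to responders.

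SAP 7.4.5 states that "DOR, and DODC will be analyzed with the same statistical methodologies as applied to OS", which means Kaplan-Meier estimates. It does not separate the two origins, and the censoring rules in SAP Table 3 do not align them.

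**The concern.** A time-to-event endpoint needs one clock start for all subjects. Here the start is chosen by best response, which is known only after follow-up. Under 6.5.1.2 as worded, a subject who has SD at the first scan and later improves to PR loses recorded disease control by improving.

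The pooled DODC median then depends partly on the mix of SD subjects and responders, and not only on how long disease was controlled. With about 20 subjects, shifts of 8 to 13 weeks in individual durations can visibly move a median.

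The wording is also uneven. Section 6.5.1.2 speaks of best response, while 7.6 speaks more loosely of a RECIST response of SD. A programmer could treat a subject with SD followed by PR either way. DODC is also to be derived per iRECIST, which the 7.6 wording does not address.

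**Working it through.** The documents give no figure for this offset, so there is none to reproduce.

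**Inputs**
- Baseline scan: *b* = 1 to 28 days before first dose (screening column of Protocol Table 2-1 and SAP Appendix A; Protocol Appendix B).
- First on-study scan: Cycle 4 Day 1, window -7 days. With 21-day cycles this is 3 × 21 = 63 days after first dose, so *s* = day 57 to 64. Scans are fixed to the calendar regardless of dose delays (footnote 5 of both schedules).
- Week-18 scan, window -14 days: *s* = day 113 to 127.
- SAP 7.1.4: a duration gains one day only if its earlier date is on or after dosing.

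**Gap for the same end day *e***
- Best response SD: *e* - 1 + *b*
- CR or PR first supported on day *s*: *e* - *s* + 1
- Difference: *b* + *s* - 2

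Results:
- Control from the first scan: 1 + 57 - 2 = **56** days to 28 + 64 - 2 = **90** days. Plain date subtraction gives 57 to 91, so the day-count convention hardly matters.
- Control first supported at week 18: 1 + 113 - 2 = **112** to 28 + 127 - 2 = **153** days. This can occur under iRECIST when iUPD is followed by iPR (example 3 of SAP Table 4, "Scenarios of Assignments of Best Overall Response using iRECIST").

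**Against PFS**, which runs from first dose and equals *e*: SD records *b* - 1 = 0 to 27 days more than PFS. A responder controlled from the first scan records *s* - 1 = 56 to 63 days less.

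**Same subject, *e* = 190, control from day 64**
- Best response stays SD: 190 - 1 + 1 = 190 to 190 - 1 + 28 = 217 days.
- Best response becomes PR: 190 - 64 + 1 = 127 days.

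**Effect on a median (illustration only).** Assume 11 uncensored subjects, so the median is the 6th value. SD subjects progress on day 127, and responders are supported from day 64 and progress on day 190. SAP 6.5.1.1 requires that "All responses will be confirmed at the subsequent tumor assessment", so a response seen on day 64 is confirmed on day 127, and day 190 (week 27) is the next scheduled scan. Under the SAP rule SD records 126 + *b* and a responder records 190 - 63 = 127.

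| Origin | Median, 4 responders + 7 SD | Median, 8 responders + 3 SD |
|---|---|---|
| SAP rule, *b* = 1 | 127 | 127 |
| SAP rule, *b* = 14 | 140 | 127 |
| SAP rule, *b* = 28 | 154 | 127 |
| First supporting scan for all (protocol) | 64 | 127 |
| Baseline scan for all, *b* = 14 | 140 | 203 |
| First dose for all | 127 | 190 |

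Responders here progress 190 - 127 = 63 days later than SD subjects. Each single-origin rule raises the median by 63 days when responders become the majority. The SAP rule leaves it flat or lowers it.

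**Limit of that illustration.** For a responder progressing on day *p*, the median falls only if *p* - 63 < 126 + *b*. That means *p* < 190, 203 or 217 for *b* = 1, 14 or 28. If responders progress one scheduled scan later, the median at *b* = 14 rises from 140 to 253 - 63 = 190 (week 36, SAP schedule) or to 274 - 63 = 211 (week 39, protocol schedule). Protocol 5.3 reports that "patients treated with pembrolizumab had an ORR of 19.1% and median duration of response 20.9 months". Applying that duration to every responder gives 20.9 × 365.25/12 = 636 days, and the median rises from 140 to 636.

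**The case against.** - **The change is prespecified and disclosed.** This is true: 7.6 states the departure from the protocol and gives a reason for SD. That reason does not explain why the same interval is not counted for responders, whose disease was also controlled during it. Disclosure does not make the pooled durations comparable.
- **Counting SD from baseline is reasonable.** It may be for SD alone. DODC combines SD with CR and PR, so whichever origin is chosen has to apply to all three.
- **The loss on improving from SD to PR depends on the reading.** This stands in part. Under the looser wording of 7.6, a responder whose first scan showed SD could also start at baseline. Section 6.5.1.2 is the explicit definition and does not allow it. The mismatch is itself a reason to fix the text.
- **The week-18 range assumes on-schedule scans.** This stands. Protocol 10.2.1.1 and Appendix C place the scan after iUPD 4 to 9 weeks later. A confirmation scan 28 days after day 57 falls on day 85, and the low end becomes 1 + 85 - 2 = 84 days. The 56 to 90 day range is untouched.
- **The practical harm is small.** The falling median needs early progression in responders and reverses with longer responses. Results are descriptive, no decision rests on DODC, and PFS already gives a common-origin measure. This limits the weight of the point. The unequal credit for equal end dates needs no scenario at all.

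**Conclusion.** The point holds. DODC as written has two time origins selected by a post-baseline outcome. For the same end date, SD records 56 to 90 more days than CR or PR when the first on-schedule scan already supports control, and 112 to 153 more when the week-18 scan is the first to do so. Equivalently, with control from the first scan, a responder must progress 56 to 90 days later than an SD subject to record the same DODC.

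These figures rest on the scheduled scan windows, the SAP 7.1.4 day count, and the reading that a responder's clock starts at an on-study scan. The direction of the effect on the pooled median is not fixed: it falls as responders increase only if they progress soon after confirmation.

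The plan should be corrected, but the reach is limited to one descriptive secondary endpoint.

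**What to change.** Use one origin for every subject with disease control, and settle it before database lock. Any of three rules removes the inequality:

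1. **First supporting assessment for all.** Delete the SD clause in SAP 6.5.1.2 and the third bullet of 7.6. This restores Protocol 12.5.2 and is the smallest edit. SD durations shorten by 56 to 90 days (112 to 153 if SD is first supported at week 18, as when iUPD is followed by iSD in Table 4, example 5). Responder durations do not change.
2. **Baseline scan for all**, declared in 7.6 as a change from the protocol. SD durations do not change; responder durations lengthen by the same ranges.
3. **First dose for all**, also declared in 7.6. SD durations shorten by 0 to 27 days; responder durations lengthen by 56 to 63 days (112 to 126 if first supported at week 18).

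If any SD-specific text is kept, use the best-response wording in both 6.5.1.2 and 7.6, and state that it covers both RECIST v1.1 and iRECIST. The cost is one derivation and the SAP wording; no new data are needed.
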